6 HYPOTHESES AND OBJECTIVES OF THE STUDY

6.1 Working hypothesis

The ophthalmic solution PRO-157 is so safe and effective in any of its different posologies when demonstrating non-inferiority when compared against Moxifloxacin and Gatifloxacin in the treatment of bacterial conjunctivitis.

Ho: The ophthalmic solution PRO-157 is not as safe and effective in any of its different dosages when it shows no inferiority when compared to Moxifloxacin and Gatifloxacin in the treatment of conjunctivitis.

Ha: The ophthalmic solution PRO-157 is so safe and effective in some of its different posologies when demonstrating non-inferiority when compared against Moxifloxacin and Gatifloxacin in the treatment of conjunctivitis.

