6.2 Objectives

General purpose:

To evaluate the safety and efficacy of the ophthalmic solution PRO-157 in three different posologies versus Moxifloxacin and versus Gatifloxacin in patients with bacterial conjunctivitis.

Specific objectives:

To determine the safety of the PRO-157 solution in three different posologies versus Moxifloxacin and versus Gatifloxacin in patients with bacterial conjunctivitis by the incidence of adverse events and visual capacity.

To evaluate the efficacy of the ophthalmic solution PRO-157 in three different posologies versus Moxifloxacin and versus Gatifloxacin in patients with bacterial conjunctivitis through conjunctival cul-de-sac culture and the clinical evaluation of some ocular signs and symptoms such as: burning, lacrimation, Foreign body sensation, pruritus, photophobia, conjunctival hyperemia, chemosis, secretion, palpebral edema, membranes and / or pseudomembranes, scales and epitheliopathy.

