• The safety of the use of PRO-157 will be evaluated in the visits indicated in the schedule, through the following parameters:

1. Visual capacity
2. Eye surface
3. Exploration of the previous segment
4. Exploration of the posterior segment
5. Burning
6. Foreign body sensation
7. Lachrymation
8. Conjunctival hyperemia
9. Itching
10. Photophobia
11. Chemosis
12. Tear discharge
13. Eyelid edema
14. Membranes / pseudomembranes
15. Scales
16. Corneal epithelial defects
17. Adverse events

It will be considered that the drug under evaluation is safe for use in humans if there are no changes in the parameters indicated in more than 5% of the subjects, in both eyes, if the

patient goes to all the visits of the study and complies with adherence to treatment $\geq 80\%$ during the time of evaluation of the study.

Variable	Operationalization	Measurement scale	Value
Visual ability	Independent Discrete quantitative	Points logMAR 0-1 0 = Snellen 20/20	Do not present change in 1 line in the Snellen letter or in 1 logarithmic point (log MAR)
Ocular surface	Dependent Qualitative ordinal	Absent Present	Abnormalities in any area of the ocular Surface
Exploration of the previous segment	Dependent Qualitative ordinal	Normal Abnormal	Abnormalities in any of the structures included: cornea, iris, pupil, irido-corneal and crystalline angle.
Exploration of the posterior segment	Dependent Qualitative ordinal	Normal Abnormal	Abnormalities in any of the structures included: vitreous, retina, macula and the optic nerve
burning	Dependent Qualitative ordinal	Absent Present	Must be recorded as absent in 95% of the subjects evaluated
strange body sensation	Dependent Qualitative ordinal	Absent Present	Must be recorded as absent in 95% of the subjects evaluated
tearing	Dependent Qualitative ordinal	Absent Present	Must be recorded as absent in 95% of the subjects evaluated

Secretion	Dependent Qualitative ordinal	Absent Present	Must be recorded as absent in 95% of the subjects evaluated
Conjunctival hyperemia	Dependent Qualitative ordinal	Absent Mild Moderate Severe	You must comply with the following: Absent ≥ 95.0% Mild ≤ 5.0% Moderate ≤ 2.5% Severe ≤ 1.0%
Photophobia	Dependent Qualitative ordinal	Absent Mild Moderate Severe	You must comply with the following: Absent ≥ 95.0% Mild ≤ 5.0% Moderate ≤ 2.5% Severe ≤ 1.0%
Chemosis	Dependent Qualitative ordinal	Absent Present	Must be recorded as absent in 95% of the subjects evaluated

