Eyelid edema	Dependent Qualitative ordinal	Absent Present	Must be recorded as absent in 95% of the subjects evaluated
Membranas Pseudomembranes	Dependent Qualitative ordinal	Absent Present	Must be recorded as absent in 95% of the subjects evaluated
Scales	Dependent Qualitative ordinal	Absent Present	Must be recorded as absent in 95% of the subjects evaluated

Epithelial defects corneal	Dependent Qualitative ordinal	Affected area, percentage	Percentage of the affected area 95%
Adverse events	Dependent Qualitative ordinal	serious Not Serious	Must be recorded as absent in 95% of the subjects evaluated

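### The safety hypothesis compares PRO-157 with moxifloxacin and gatifloxacin, but the only rule for a safety conclusion is an observed 5% cut-off on PRO-157 alone, with no comparator, margin or interval

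*Combined protocol and SAP*

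**What the plan says.** Section 6.1 states the aim as safety and efficacy of PRO-157 "when demonstrating non-inferiority when compared against Moxifloxacin and Gatifloxacin in the treatment of bacterial conjunctivitis". The null hypothesis has the same comparative form: "Ho: The ophthalmic solution PRO-157 is not as safe and effective in any of its different dosages". No margin for safety is given there or anywhere else.

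The specific safety objective in section 6.2 is also comparative: "To determine the safety of the PRO-157 solution in three different posologies versus Moxifloxacin and versus Gatifloxacin", judged by adverse-event incidence and visual capacity.

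Section 7.1 then sets the decision rule. It opens with "The safety of the use of PRO-157 will be evaluated in the visits indicated in the schedule", lists 17 parameters, and says the drug under evaluation counts as "safe for use in humans if there are no changes in the parameters indicated in more than 5% of the subjects". A further condition is that the "patient goes to all the visits of the study and complies with adherence to treatment" of at least 80%. In the table that follows, the adverse-event row and most of the sign and symptom rows carry their own mark: "Must be recorded as absent in 95% of the subjects evaluated".

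Section 23 sizes the study on efficacy of active drug against placebo. Under its heading on analysed data sets, the ITT population is used to describe the variables, and a bivariate analysis, not further specified, is planned in the PP population. Section 15.3 keeps the data of withdrawn subjects for a safety analysis in the ITT population.

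**The concern.** The question and the decision rule do not match. The question is whether PRO-157 is as safe as two active drugs. The rule asks whether the observed percentage in PRO-157 stays at or below a fixed mark. The moxifloxacin and gatifloxacin arms, although randomised and followed on the same schedule, play no part in it.

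Two consequences follow. First, the verdict can run against the observed comparison in either direction. Second, a raw percentage from about 60 subjects carries wide uncertainty. A pass would be read as showing a rate of 5% or less, which it does not show.

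This does not depend on how the other details of the rule are settled. If the direction of change, the choice of signs and the adherence condition were all made precise, the rule would still be single-arm and without an interval.

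**Working it through.** **Inputs.** The 5% mark and the 95%-absent mark come from section 7.1. The size of 60 eyes per group comes from the summary and section 8. Three PRO-157 posologies and two comparators come from section 8. The number of subjects per arm is not stated. I assume 60 independent subjects first and then vary that.

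**The plan's own figures.** The only calculated figures are in Annex 1 of section 23: 147 and 44 per group. The Fleiss formula with z = 1.960 and 0.842 gives m' = 135.3 and a corrected 147.2 for 69.8% against 53.3%, and m' = 36.4 and a corrected 43.7 for 92.34% against 66.12%. Both reproduce. Both concern efficacy against placebo, and no precision or power is given for safety.

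**Largest passing count.** 0.05 × 60 = 3, so 3/60 = 5.0% passes and 4/60 = 6.7% fails.

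**What a pass excludes (one parameter, one arm).** Exact (Clopper-Pearson) 95% upper limits, solving P(X ≤ x | n = 60, p) = 0.025 for p:

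| Events | Upper limit |
|---|---|
| 0/60 | 1 - 0.025^(1/60) = 6.0% |
| 1/60 | 8.9% |
| 2/60 | 11.5% |
| 3/60 | 13.9% (lower limit 1.0%) |

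Every passing result has an upper limit above 5%.

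**Effect of the denominator.** The plan counts eyes, but the rule is stated in subjects. If 60 eyes come from 30 to 60 subjects, the largest passing count is 1 for n = 30 to 39, 2 for n = 40 to 59, and 3 for n = 60. The upper limit at that count does not move steadily with n: 17.2% at 1/30, 13.5% at 1/39, 16.9% at 2/40, 11.7% at 2/59, 13.9% at 3/60. The range is about 12% to 17%.

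**Chance of passing on one parameter.** P(X ≤ 3 | 60, p) = Σ C(60,k) p^k (1-p)^(60-k), k = 0 to 3:

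| True rate | Pass |
|---|---|
| 5% | 64.7% |
| 8% | 28.3% |
| 10% | 13.7% |
| 14% | 2.4% |

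**Verdict against comparison.** Newcombe 95% CI for p1 - p2 = d, from the Wilson limits (l, u) of each arm: lower d - √[(p1 - l1)² + (u2 - p2)²], upper d + √[(u1 - p1)² + (p2 - l2)²].

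- PRO-157 3/60 (Wilson 1.7% to 13.7%) against 0/60 (0% to 6.0%): d = +5.0 points. Lower = 5.0 - √(3.29² + 6.02²) = -1.9; upper = 5.0 + 8.7 = +13.7. The rule says safe.
- PRO-157 4/60 (2.6% to 15.9%) against 6/60 (4.7% to 20.1%): d = -3.3 points. Lower = -3.3 - √(4.04² + 10.15²) = -14.3; upper = -3.3 + √(9.26² + 5.34²) = +7.4. The rule says not safe.

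Neither interval excludes zero. The examples show that the verdict need not follow the observed comparison. They do not show that the drugs differ.

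**The case against.** **An absolute mark can stand beside a comparative hypothesis.** A phase II study may reasonably set an acceptability threshold for the new drug and need not be powered for a safety test. This stands, and the 5% mark need not be deleted. What is missing is any comparative safety analysis tied to the conclusion. A study too small for a safety test also has less reason to issue a yes-or-no verdict.

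**Between-arm data will exist.** The comparator arms are there, a bivariate analysis is mentioned, and section 15.3 already assigns safety to the ITT population. A reader might infer that the plan collects nothing comparative on safety or ignores withdrawn patients altogether. The documents do not support that. However, the bivariate analysis is unspecified, sits in the PP set, and is not linked to the safety conclusion.

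**The 14% figure is the limiting case.** A reader might infer that any safe verdict leaves rates near 14% open. That is true only of exactly 3/60 in one arm on one parameter. With fewer events the limit is lower, and a true rate of 14% would pass only 2.4% of the time. Pooling the three posologies at 9/180 would give an upper limit of 9.3%, but no pooling is planned.

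**The pass probabilities are per parameter.** The rule covers 17 parameters. If all must be met, an overall pass is harder. For scale, assuming independence, two parameters at a true 8% both pass 0.283² = 8% of the time. A reader might take 28% or 14% as the chance of an overall safe verdict; as the rule is written, that would overstate it.

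**Fewer subjects do not always mean a wider interval.** Because the passing count falls in steps, 2/59 gives a lower upper limit (11.7%) than 3/60 (13.9%). Only the range of about 12% to 17% can be claimed.

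**Conclusion.** The concern holds as a mismatch between a comparative safety question and a single-arm decision rule without an interval. Following section 7.1 as written can produce a safe or not-safe verdict that leaves the hypothesis in section 6.1 and the objective in section 6.2 unanswered. Nothing in section 23 repairs this.

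No pass at 60 subjects per arm demonstrates a rate of 5% or less: the upper 95% limit on one parameter runs from 6.0% with no events to 13.9% with three. The 60 independent subjects are an assumption, because the plan gives eyes and not subjects.

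The point does not show that PRO-157 is unsafe, that the rule would readily pass a drug with a 14% event rate, or that the trial must be larger. It should be corrected before the analysis, using data the study already collects.

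**What to change.** In sections 7.1 and 23, specify the following in the ITT (all treated) population that section 15.3 already assigns to safety:

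- adverse-event incidence and visual-capacity worsening per arm, each with an exact 95% CI, counted per subject;
- each PRO-157 posology minus each comparator (3 × 2 = 6 differences per measure) with a 95% CI, for example Newcombe.

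Base the comparative safety conclusion on those intervals, and state the size of difference that the data exclude. The 5% mark may stay as a descriptive benchmark per arm, shown with its interval and not as the verdict. Claim non-inferior safety only against a margin stated in advance; otherwise word the safety conclusion as descriptive.

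The cost is wording in two sections and one extra table, with no new data or patients. The downside is a weaker claim than a plain statement that the drug is safe.

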An artificial lagrima without conservative Lagricel Ofteno® will also be applied one drop 4 times a day to all patients who enter the study during the 7 days of treatment with the study medication.

The valuation days indicated in Figure 1 of the Study Plan must be carefully observed. A variation of ± 1 days can be accepted in relation to the inclusion visit (from day 1 to 8). In the case of the inclusion of subjects from 0 years to less 18 years minus 1 day, they will be included progressively as follow:

- Age group of 12 to 18 years.
- Age group from 2 to 12 years old.
- Age group from 0 to 12 years old.

This with the intention of integrating patients once the dosage parameters have been established as safe and recommended for the younger age groups.

The indications of the inclusion periods will be made as the results are gathered in the groups of minors.

Blinding

The double-blind study is a procedure in which the patient and the attending physician do not know which of the intervention groups was assigned by the study patient. The blinding codes are protected by a person outside the study.

Figure 1 - Plan of the Study

[figure not shown]

Table 2: Timeline

Procedimiento	Visita Basal				
		Visita 1	Visita Final	Seguimiento Telefónico EA	Visita no programada / Descontinuación
	Día 1	Día 3	Día 8	Día 23	
Criterios de Elegibilidad	X				
Firma de consentimiento informado	X				
Datos demográficos	X				
Prueba de embarazo en orina (si aplica)	X		X		
Historia Clínica General y Oftalmológica	X				
Padecimiento actual					X
Toma de muestra para cultivo	X		X		
Fotografía clínica de los ojos	X	X	X		
Asignación de número al paciente	X				
Entrega de medicamento	X				
Inicio de aplicación de medicamento	X				
Aplicación de medicamento	X	X	X		
Devolución de medicamento por parte del paciente			X		
Sintomatología Ocular (A,B,C,D)	X	X	X		X
Agudeza y/o Capacidad Visual	X	X	X		X
Biomicroscopia anterior (F,G,H,I,J,K)	X	X	X		X
Tinciones de fluoresceína/verde de lisamina	X	X	X		
Revisión del segmento posterior (L,M,N,O)	X	X	X		X
Evaluación de eventos adversos	X	X	X	X	X
Evaluación de medicamentos concomitantes	X	X	X		X

A) Burning B) Lachrymation C) Foreign body sensation D) Pruritus E) Photophobia DF) Conjunctival hyperemia G) Chemosis H) Secretion I) Eyelid edema J) Membranes and / or pseudo-membranes K) Epitheliopathy L) Vitreous M) Retina N) macula O) optic nerve.

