- Any complication or lack of control that the doctor considers should be treated differently.

- **Elimination Criteria**

- Clinicians:

a. Any complication or lack of control that the doctor considers should be treated differently. The following points should be considered:

i. The no improvement of the initial clinical signs and symptoms.

ii. Diagnosis added or different to that of acute bacterial conjunctivitis.

iii. Use other medications outside the study.

b. * It is reiterated that they are minimum parameters to be considered, any other case in which the investigator considers necessary the elimination of the patient and suspension of the treatment must be informed and evaluated by the sponsor.

- For the sponsor:

- a. By its will, it will not have penalties, nor will it lose benefits to those that it already has right.
- b. For the total term of the scheduled visits in the clinical study.
- c. For a serious adverse event related to the medication that endangers your health.
- d. Why the medication does not work at the doctor's discretion.

and. Why, by sponsor's decision, the study ends earlier.

In case of withdrawal for any of these reasons or any other at the discretion of your doctor, you will be prescribed again the medication of which you were already a user or any other that is of benefit for your best treatment.

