15.3 Criteria for the premature withdrawal of the subject

Criteria for premature withdrawal

The following criteria will cause a mandatory withdrawal from the study:

The reasons for a patient leaving the study prematurely may be the following:

- Subject's decision. The patient who wishes to leave the study for any reason can do so at any time, but must inform the researcher. In all cases, the investigator should attempt to establish contact with the patient as soon as possible for a final evaluation in order to:
 - Document the patient's decision in clinical notes,
 - Obtain the reason (s) for the exit and write them down in the FRC exit format,
 - Evaluate the patient's clinical status,
 - If necessary, take the appropriate therapeutic measures: management of an adverse event.

In case of failure of all these attempts to contact the patient, the investigator may declare "loss of follow-up" of the patient. The investigator will document all the attempts in the corresponding medical file.

- Decision of the investigator. Especially if an adverse event occurs and the researcher considers that this may threaten the patient's health, or if an important disease occurs that requires the prescription of a medication incompatible with the objective of the study.
- Need for another treatment according to the criteria of the Medical Investigator who will have to document it well in his notes.
- Pregnancy (see procedure in Appendix 2)
- Any deviation to the protocol that affects the patient's safety.
- In all cases, the available data will be saved for the safety analysis (population evaluable by intention to treat).

Process

Whatever the reason for the premature discontinuation of the study treatment, the investigator should immediately inform Laboratorios Sophia S.A. of C.V. and the patient must return the rest of the study treatments to the center.

In case of premature withdrawal of treatment, the investigator should record the reason (s), the exact date of the premature discontinuation of the treatment in the source document and in FRC. If more than one reason is given, the investigator must indicate the main reason.

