$Z_{1-\alpha/2} = Z_{0.975}$ de la distribución normal estandarizada que deja un area de 0.975 a la izquierda. Implica una confiabilidad del 95% 1.960

β = Probabilidad de error tipo 2 0.200

$1-\beta$ = Percentil unilateral para la beta asignada 0.800

$Z_{1-\beta} = Z_{0.80}$ de la distribución normal estandarizada que deja un area de 0.80 a la izquierda. Implica un poder del 80% 0.842

m' = Tamaño de muestra

$$m' = \frac{(z_{1-\alpha/2} \sqrt{(r + 1) * P * Q} + z_{1-\beta} \sqrt{r * P1 * Q1 + P2 * Q2})^2}{r * (P2 - P1)^2}$$

$$m' = \frac{(1.960 \sqrt{(1.00+1) 0.79 * 0.21} + 0.842 \sqrt{1.00 * 0.92 * 0.08 + 0.66 * 0.34})^2}{1.00 (0.66 - 0.92)^2}$$

$$m' = 36.373$$

m = Tamaño de muestra corregido

$$m = 0.25 m' * \left[1 + \sqrt{1 + \frac{2(r + 1)}{m' * r * |P2 - P1|}} \right]^2$$

$$m = 44 \quad \begin{array}{l} \text{Tamaño de muestra para el grupo de referencia (Controles): } m_1 = r * m \\ \text{Tamaño de muestra para el grupo de estudio (Casos): } m_2 = m \end{array} \quad \begin{array}{l} 44 \\ 44 \end{array}$$

Analyzed data set

The data will be analyzed in two groups, one will be made up of the population evaluable by Intention to Treat (ITT) in which each of the variables is described, the ITT population will be constituted by all the recruited subjects who have received at least one dose of study treatment.

Others will be the evaluable population Per Protocol (PP) which is the subset of ITT composed of all subjects without any major deviation from the protocol, in which the bivariate analysis will be performed.

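### The Section 7.1 rule for calling the drug safe is conditional on full attendance and 80% adherence, which conflicts with the ITT safety analysis in Section 15.3

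*Combined protocol and SAP*

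**What the plan says.** **Rule for safe (Section 7.1).** After a list of 17 parameters, the last being adverse events, the drug is to be considered safe "if there are no changes in the parameters indicated in more than 5% of the subjects". The same sentence adds that this applies if the "patient goes to all the visits of the study and complies with adherence to treatment" of at least 80%. In the table that follows, the adverse-event row sets the limit "Must be recorded as absent in 95% of the subjects evaluated".

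**Withdrawal for harm.** The elimination criteria at the end of Section 15.2 include removal "For a serious adverse event related to the medication that endangers your health". Section 15.3 lets the investigator withdraw a patient: "Especially if an adverse event occurs and the researcher considers that this may threaten" the patient's health.

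**Data of withdrawn patients (Section 15.3).** "In all cases, the available data will be saved for the safety analysis (population evaluable by intention to treat".

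**Analysis sets (Section 23).** ITT is "all the recruited subjects who have received at least one dose of study treatment" and is the set in which the variables are described. The per-protocol set is the part of ITT without major deviations, and the bivariate analysis is done there.

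**Entry of younger children (Sections 8 and 15.1).** Minors enter in descending age bands: "This with the intention of integrating patients once the dosage parameters have been established as safe and recommended for the younger age groups". Neither section says what safe means here, and neither cites Section 7.1.

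**The concern.** A safety conclusion should rest on everyone exposed. In the text available for review, the Section 7.1 sentence is the only statement of when the drug counts as safe. Its attendance and adherence condition is most likely to fail in patients harmed enough to stop. If the condition defines who is counted, the rule sets no limit on how many patients may stop for adverse events, and it can be met by a badly tolerated posology. Section 15.3 points to the opposite population. The plan can then support two different safety verdicts on the same data, with nothing said in advance about which one stands. The incidence of adverse events is a specific objective of the trial (Section 6.2), so the choice should not be left until results are known.

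**Working it through.** **1. Inputs from the plan.** The limit is 5% of subjects (Section 7.1), which agrees with the adverse-event row: 100% − 95% = 5%. Treatment lasts 7 days at 2, 3 or 4 drops a day, with visits on days 1, 3 and 8 (Section 8). Each arm has 60 eyes, so 30 to 60 patients depending on whether one or both eyes qualify. The plan gives no calculation for the safety rule, and the sample-size figures in Section 23 do not bear on it.

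**2. Who fails the condition.** Planned drops per eye are 7 × 2 = 14, 7 × 3 = 21 or 7 × 4 = 28. Eighty per cent of these is 11.2, 16.8 or 22.4. Stopping after day 5 gives 10, 15 or 20 drops, that is 5/7 = 71.4%, so the adherence condition fails at every posology. A patient withdrawn from the study before the day 8 visit also fails the attendance condition, whatever the adherence.

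**3. The two readings beside Section 15.3.**
- *Denominator rule:* only patients with all visits and at least 80% adherence count. Patients who stop early for an event leave both numerator and denominator. Section 15.3 keeps them.
- *Requirement on every patient:* one missed visit or one poor adherer prevents a safe verdict. Section 15.3 expects withdrawals and still plans a safety analysis.

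**4. Effect of the first reading on the adverse-event limit (illustrative counts).**
- 60 patients, 6 stop for an event, 2 others have one: 2/(60 − 6) = 2/54 = 3.7%, limit met. All treated: (2 + 6)/60 = 13.3%, limit not met.
- 30 patients, 3 stop for an event, 1 other has one: 1/(30 − 3) = 1/27 = 3.7%. All treated: (1 + 3)/30 = 13.3%.
- Smaller case, 60 patients, 4 with events of whom 2 stop: 2/58 = 3.4% against 4/60 = 6.7%.

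**5. How the gap depends on stopping.** Let W ~ Bin(60, w) be the number who stop for an event, and A ~ Bin(60 − W, 0.02) the number of events among the rest. The first reading meets the limit if A ≤ 0.05(60 − W). All treated meets it if A + W ≤ 3. The 2% rate and the values of w are assumptions.

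| w | Limit met, first reading | Limit met, all treated |
|---|---|---|
| 0 | 0.968 | 0.968 |
| 1% | 0.93 | 0.90 |
| 2% | 0.91 | 0.79 |
| 5% | 0.898 | 0.399 |
| 10% | 0.906 | 0.066 |
| 20% | 0.928 | 0.0004 |

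A different model fixes the total event rate at 10% in 60 patients and lets half of the affected patients stop. It gives 0.428 against 0.137. The direction is the same and the gap is smaller than in the 10% row.

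**The case against.** The plan looks after withdrawn patients in several places. Section 15.3 keeps their data in all cases and asks for a final evaluation and follow-up of the event. The schedule has an unscheduled/discontinuation visit with adverse-event assessment. Section 20 follows every event to completion. A 5% limit on an observed proportion is a description, and Section 23 describes variables in ITT. The adverse-event row in Section 7.1 refers to subjects evaluated, with no attendance or adherence condition. The safety sentence also reads as a rough translation, and its conditional clause need not define a denominator.

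Most of this stands, and it rules out one stronger reading: that events in patients who stop are lost from the trial. They are recorded and belong to an ITT safety analysis. None of it removes the condition from the one sentence that says when the drug is safe.

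Two other inferences are tempting and unsupported:
- *Younger children are admitted on a completers-only rule.* Sections 8 and 15.1 do not cite Section 7.1. Its sentence reads as a conclusion about the drug, not an interim check. What the text shows is that the age steps have no stated criterion.
- *The table gives the chance that the drug is called safe.* It covers one of 17 parameters. Several others are signs and symptoms that patients have at entry, most with a limit of absence in 95%, so the overall chance is lower. The larger stopping rates are also severe: with 2% events among the rest, w = 10% means that 0.10/(0.10 + 0.90 × 0.02) = 85% of affected patients stop. The phase I study in healthy volunteers reported no adverse events (Section 5).

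**Conclusion.** The point holds as a conflict within the plan. Section 7.1 ties the safe verdict to attendance and adherence, Section 15.3 calls for safety in ITT, and Section 23 does not reconcile them for this rule. The direction of error depends on the reading: too lenient if the condition defines the denominator, too strict if it binds every patient. Neither is a usable safety rule.

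For the adverse-event limit under the first reading, the difference can reverse the result (3.7% against 13.3% in the 60-patient example). It is modest when 1% to 2% of patients stop for an event and absent when none do. These sizes rest on assumed event and stopping rates; only the 5% limit, the 7-day course and the arm size come from the plan. The bearing on paediatric entry is an inference: Section 7.1 is the only definition of safe in the text available, so it is the natural rule to apply, but the plan does not say so.

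**What to change.** - **Section 7.1:** delete the all-visits and 80% adherence condition from the safety sentence and write: *Safety is judged in all subjects who received at least one dose (ITT, Section 23); a subject who stops or is withdrawn because of an adverse event counts as having one.*
- **Section 23:** state that adverse events are summarised and compared between arms in the ITT set.
- **Sections 8 and 15.1:** say that safe means the corrected Section 7.1 rule, applied to all treated minors of the older age group.

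Adherence can still be reported and used to define the per-protocol set. The cost is wording in four sections. No patients, visits or measurements are added, because Section 15.3 already requires the withdrawn patients' data to be kept for the safety analysis.
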